4.5.7 Assessment of Disability: Expanded Disability Status Scale

Disability in MS is commonly measured by the EDSS. EDSS will be administered by the Examining Investigator at the timepoints indicated in the schedule of activities (see [Appendix 1](#), [Appendix 2](#), [Appendix 3](#) and [Appendix 4](#)). The EDSS will be assessed in all patients by the Examining Investigator at screening, baseline, and every 12 weeks (regularly scheduled visit) during the double-blind treatment and FU1 phases; every 24 weeks during the OLE phase; at any unscheduled visit; and at treatment discontinuation, end of observation, or withdrawal from follow-up visit. Additional EDSS assessments for individual patients may be requested between visits (i.e., during an MS relapse, neurological worsening, etc.). All FSS and total EDSS scores will be captured electronically.

EDSS CDP is defined as an increase of ≥ 1.0 point from the baseline EDSS score that is not attributable to another etiology (e.g., fever, concurrent illness, or concomitant medication) when the baseline score is ≤ 5.5 and ≥ 0.5 point when the baseline score is > 5.5 . Disability progression is considered confirmed when the increase in the EDSS score is confirmed at a regularly scheduled visit at least 12 weeks after the initial documentation of the progression. A 24-week CDP requires that the increase in EDSS score be confirmed at least 24 weeks after the initial documentation of the progression.

The EDSS is based on a standard neurological examination, incorporating functional systems (pyramidal, cerebellar, brainstem, sensory, bowel and bladder, visual, and cerebral [or mental]) and ambulation rated and scored as FSS. Each FSS is an ordinal clinical rating scale ranging from 0 to 5 or 6. These ratings are then used in conjunction with observations and information concerning ambulation and use of assistive devices to determine the EDSS score. The EDSS is a disability scale that ranges in 0.5-point steps from 0 (normal) to 10.0 (death) (Kurtzke 1983; Kappos 2011). Note that the following

items need not be scored: sexual dysfunction and fatigue and consequently should not contribute to the Cerebral FS score nor EDSS step.

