4.7.2 Patient Discontinuation from Study

Patients will return to the clinic for an end of observation or withdrawal from follow-up visit.

Patients have the right to voluntarily withdraw from the study at any time for any reason. In addition, the investigator has the right to withdraw a patient from the study at any time. Reasons for withdrawal from the study may include, but are not limited to, the following:

- Patient withdrawal of consent
- Study termination or site closure

Every effort should be made to obtain information on patients who withdraw from the study. The primary reason for withdrawal from the study should be documented on the appropriate eCRF. If a patient requests to be withdrawn from the study, this request must be documented in the source documents and signed by the investigator. Patients who withdraw from the study will not be replaced.

Patients who withdraw from study drug treatment during any study period, for any reason, are encouraged to enter and complete the applicable follow-up phase (see Section [4.7.1](#)). Patients who withdraw from FU1 or FU2 will return to the clinic for a withdrawal from follow-up visit (see [Appendix 2](#) and [Appendix 4](#) for additional details). If a patient discontinues from the study, the patient should be asked if he or she can still be contacted for further information, unless otherwise specified by the local requirements. The outcome of that discussion should be documented in both the medical records and in the eCRF. If lost to follow-up, the investigator should contact the patient or a responsible relative by telephone followed by registered mail or through a personal visit to establish as completely as possible the reason for the withdrawal. A complete final evaluation at the time of the patient's withdrawal should be made with an explanation of why the patient withdrew from the study.

When applicable, patients should be informed of circumstances under which their participation may be terminated at the medical discretion of the investigator without their

consent. Any administrative or other reasons for withdrawal must be documented and explained to the patient.

An excessive rate of withdrawals can render the study non-interpretable; therefore, unnecessary withdrawal of patients should be avoided. Should a patient decide to withdraw, all efforts will be made to complete and report the observations prior to withdrawal as thoroughly as possible.

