Appendix 2 Schedule of Activities: Follow-Up 1 (and PDP OCR)

	FU1 ^a						Delayed Dosing Visit ^b	Unsched. Visit ^c	Tx Discon. Visit ^d	EOO or WD from FU
	Follow-up	PDP OCR								
Dose Visit	Visits every 12 wk (± 7 d)	1			N ^e					
Study week		1	2	3	n	n				
(Window in days)		0	2	12	n	n+ 12wk				
			±2	±7	±5	±7				
Informed consent ^f		x								
PROs (ABILHAND, Neuro-QoL-UE, MFIS, MSIS-29) (every 48 weeks) ^g	(x)	x			(x)				x	
PGIC-F, PGIC-UL (every 48 weeks) ^g	(x)	x			(x)				x	
EQ-5D-5L (every 48 weeks) ^g		x			(x)				x	
Vital signs ^h		x	x	x	x		x			
Physical examination ⁱ	x	x			x		x		x	x
Neurological examination ^j	x	x	x	x	x	x	x	x	x	x
9-HPT ^k	x	x		x	x	x		x	x	x
EDSS ^l	x	x		x	x	x		x	x	x
SDMT	x	x			x			x	x	x
Hematology, chemistry, urinalysis ^m	x	x		x	x	x			x	x
Flow cytometry (including CD3/4/8/19 count) ⁿ	x	x	x		x		x		x	x
CD4				x		x				
IgG, IgA, IgM	x	x		x		x			x	
Pregnancy test (if applicable) ^o		x	x		x		x			
Review of re-treatment criteria		x	x		x		x			
Pretreatment with IV methylprednisolone and antihistaminic ^p		x	x		x		x			
Administration (infusion) of ocrelizumab ^q		x	x		x		x			

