4.2.1 Definition of Primary Endpoint

The primary efficacy endpoint is time to onset of composite 12-week CDP defined as the time from randomization to the first occurrence of at least one of the following progression events:

- **C1:** 12-week CDP in 9-HPT, defined as a 20% worsening from baseline in 9-HPT confirmed for at least 12 weeks
- **C2:** 12-week CDP in EDSS score, defined as an increase of ≥ 1.0 point from baseline EDSS score in patients with a baseline EDSS score ≤ 5.5 or an increase of ≥ 0.5 point in patients with a baseline EDSS score of >5.5 that is confirmed for at least 12 weeks

Initial disability progression can occur at any visit, including unscheduled visits. Four conditions must be fulfilled to satisfy the 12-weeks confirmation criteria for disability progression based on C1 and C2:

1. The confirmation (of disability progression) visit must be at least 12 weeks (84 days) after the initial disability progression.
2. The confirmation visit must be either a scheduled or treatment discontinuation visit.
3. Assessments within 30 days after the onset of a protocol-defined relapse cannot be used for confirmation of the progression.
4. All EDSS or 9-HPT assessments between the initial disability progression and the confirmation visit should also fulfill the requirements of disability progression, i.e., ≥ 1.0 point increase in baseline EDSS if baseline EDSS ≤ 5.5 or ≥ 0.5 increase if baseline EDSS >5.5 , or $\geq 20\%$ increase in 9-HPT from baseline.

If any of the four criteria listed above are not satisfied, then the initial disability progression is not the onset of composite 12-week CDP.

In criteria 3, a protocol-defined relapse is defined as the occurrence of new or worsening neurological symptoms attributable to MS and immediately preceded by a relatively stable or improving neurological state of at least 30 days. Symptoms must persist for at least 24 hours and should not be attributable to confounding clinical factors (e.g., fever, infection, injury, adverse reactions to concomitant medications). The new or worsening neurological symptoms must be accompanied by objective neurological worsening consistent with an increase of at least one of the following:

- Half a step (0.5 point) on the EDSS
- Two points on one of the selected FSS as listed below
- One point on two or more of the selected FSS as listed below

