Withdrawal from treatment and initiation of another MS DMT or commercial ocrelizumab: Future disease progression in the hypothetical scenario as if no other therapy had been initiated is predicted on the basis of previously observed data and the preceding reason for withdrawal from study treatment.

The following strategies will be used:

- If the patient withdraws from study treatment due to lack of efficacy, a disability progression event will be imputed at the time of initiation of another treatment.

Ocrelizumab—F. Hoffmann-La Roche Ltd

Statistical Analysis Plan WA40404

- Withdrawal from study treatment due to another reason will be:
 - Imputed as a disability progression event if the patient had an initial disability progression at the date of his or her last EDSS or 9-HPT assessment prior to the initiation of another treatment, whichever is the earliest
 - Censored in all other cases at the date of the last EDSS or 9-HPT assessment prior to the initiation of another treatment, whichever is the earliest

For each component (EDSS and 9-HPT), missing assessments at scheduled visits prior to the last assessment of a patient, i.e. intermediate missing data, will not be imputed. For patients with initial disability progression based on EDSS or $\geq 20\%$ increase in 9-HPT, data collected at the next scheduled visit or treatment discontinuation visit will be used to confirm disability progression.

Every effort is made to keep the patients in the study after they withdraw from treatment, however if patients withdraw their consent to participate in the study their data will be missing after study withdrawal.

Missing data following withdrawal from study with withdrawal from treatment due to lack of efficacy will be imputed as a disability progression event at the time of withdrawal from the study.

Missing data following withdrawal from study with withdrawal from treatment due to another reason will be:

- Imputed as a disability progression event if the patient had an initial disability progression at the date of his or her last EDSS or 9-HPT assessment, whichever is the earliest
- Censored in all other cases at the date of the last EDSS or 9-HPT assessment, whichever is the earliest

Patients without any disability progression events (including imputed events) during the double-blind treatment period will be censored at the date of the last EDSS or 9-HPT assessment during the double-blind treatment period, whichever is the earliest.

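### The SAP's confirmation rule leaves out the end-of-observation / withdrawal-from-follow-up visit, so a progression observed for 12 weeks or more at that visit is handled as imputed, not confirmed (minor)

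*Protocol*

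**What the plan says.** **Where disability is assessed.** The FU1 schedule (Protocol Appendix 2) marks both 9-HPT and EDSS in its last column, "EOO or WD from FU". Protocol 4.5.7 lists the 12-weekly regularly scheduled EDSS assessments and then, separately, those "at treatment discontinuation, end of observation, or withdrawal from follow-up visit". Protocol 4.7.2 adds: "Patients who withdraw from FU1 or FU2 will return to the clinic for a withdrawal from follow-up visit". Until the primary analysis, these assessments are made by the blinded Examining Investigator (Protocol 4.2).

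**What can confirm a progression.** SAP 4.2.1 is generous about onset: "Initial disability progression can occur at any visit, including unscheduled visits". It sets four conditions for confirmation. Condition 1 is "The confirmation (of disability progression) visit must be at least 12 weeks (84 days) after the initial disability progression". Condition 2 is "The confirmation visit must be either a scheduled or treatment discontinuation visit". Conditions 3 and 4 exclude assessments soon after a relapse and require every intermediate assessment to show progression. Failing any one of the four means the initial progression is not the onset of the composite event. SAP 4.2.2 repeats the visit list: "data collected at the next scheduled visit or treatment discontinuation visit will be used to confirm disability progression". SAP 4.4.4 has a matching sentence. Protocol 6.4.1 names only regularly scheduled visits, but the SAP states that it supersedes the protocol.

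**What happens when a patient leaves the study.** Under SAP 4.2.2, if treatment was stopped for lack of efficacy, an event is imputed at the time of study withdrawal. If it was stopped for another reason, an event is imputed when there was an initial progression at the last EDSS or 9-HPT assessment; otherwise the patient is censored.

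**The concern.** The SAP accepts one exit visit for confirmation, treatment discontinuation, and leaves out two others at which the same tests are done by the same blinded examiner. Two patients with identical data, progressed at one visit and still progressed at least 84 days later, are classified differently according to the label on the second visit. One is a confirmed event dated at onset. The other depends on the missing-data rules.

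The patients concerned have stopped treatment and then left FU1, which is the group on whom the treatment-policy handling relies. At stake are how the primary event is derived, its date, and whether the sensitivity analysis varies something that was actually observed.

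**Working it through.** No figure in the plan depends on this rule, so the main check is to apply the rules to a patient.

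**1. The patient.** In FU1 and on no other MS therapy. Progression is first documented at a 12-weekly visit, and the next assessment is the exit visit at least 84 days later, still progressed. Conditions 1, 3 and 4 are taken as met.

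| Visit at which sustained progression is seen | SAP 4.2.1 | SAP 4.2.2 | Result in primary analysis |
|---|---|---|---|
| Scheduled or treatment discontinuation | Confirmed | Not needed | Event, dated at onset |
| Withdrawal from FU1; treatment stopped for lack of efficacy | Condition 2 fails | Imputed at study withdrawal | Event, dated at least 12 weeks after documented onset |
| Withdrawal from FU1; treatment stopped for another reason | Condition 2 fails | Imputed if progressed at last assessment | Event on the plain reading |
| End of observation without study withdrawal | Condition 2 fails | No rule applies | Not an event, unless the visit is taken to be a scheduled one |

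**2. Tipping point.** SAP 4.2.3 item 1 takes the third row's patients and draws their event status with probability from 0 to 1. At 0, a progression observed for 84 days or more is censored.

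**3. Wording.** SAP 4.2.1 uses initial progression for the first documentation, from which the 84 days run. In the third row that documentation came before the last assessment, not at it. Read literally, SAP 4.2.2 would censor this sustained progression while imputing an event for one first seen at the exit visit.

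**4. Who is outside the problem in the primary analysis.** Patients who started another MS therapy or commercial ocrelizumab are imputed or censored at that earlier point. PDP OCR patients already have a confirmed progression (Protocol 6.4.1.1). The first group does matter for the treatment-policy supplementary estimand (SAP 4.2.4 item 2), which uses their later FU1 data and states no imputation rule.

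**5. Size.** Power = Φ(√(D/4) × |ln HR| − z), with D events, 1:1 allocation and z the two-sided critical value. The plan's figures reproduce:
- D = 340, HR 0.70, alpha 0.0146: 9.220 × 0.3567 − 2.442 = 0.846, giving 80.1% (plan: 80%).
- D = 340, HR 0.75, alpha 0.05: 9.220 × 0.2877 − 1.960 = 0.692, giving 75.6% (plan: 75.5%).
- D = 122, HR 0.60, alpha 0.04: 5.523 × 0.5108 − 2.054 = 0.767, giving 77.9% (plan: 78%).

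If 1%, 2% or 5% of the 340 events were lost, power at HR 0.70 would be 79.7%, 79.2% or 77.7%.

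The documents give no rate of leaving FU1, so a count needs assumptions:
- The 10% annual dropout is read as stopping treatment: 144 weeks is 2.76 years, and 1 − 0.90^2.76 = 25.2%.
- 25% to 50% of these later leave FU1 (assumed).
- Progression per 12 weeks, from 40% at Week 120: 1 − 0.60^(12/120) = 5.0% on placebo, and 1 − 0.60^(0.70 × 12/120) = 3.5% at HR 0.70.
- Every leaver attends an exit visit at least 84 days after onset (assumed).

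The count is then 1000 × 0.252 × 0.25 × 0.035 = 2.2 to 1000 × 0.252 × 0.50 × 0.050 = 6.3 patients, under 2% of 340. It would double if leavers progress twice as fast. These are patients touched by the rule; steps 1 to 3 show that most are not lost as events.

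**The case against.** A reader might infer that progression sustained at the exit visit is not a primary event, so that events are lost selectively and the hazard ratio is biased. The documents do not support that. FU1 consists of patients who stopped treatment early, so anyone withdrawing from the study in FU1 falls under one of the two imputation rules in SAP 4.2.2. Protocol 6.4.1.1 describes the second group as having progressed just before withdrawal, and SAP 4.2.3 describes them as patients whose progression is assumed to have gone on to be confirmed. Both point to the plain reading, under which they are events. The 12- and 24-week secondary endpoints use the same estimation method and inherit the imputation.

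The end-of-observation case is also thin. FU1 patients still ongoing at Week 144 or at the primary analysis move to FU2, Week 144 falls on the 12-weekly grid, and the FU2 schedule (Protocol Appendix 4) marks no EDSS or 9-HPT. Nor does any section say that a 12-weekly visit stops being a scheduled visit because the patient leaves at it.

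One could also defend the narrow list on principle: confirmation at pre-planned visits avoids timing chosen by the patient. But the treatment discontinuation visit has the same property, and the SAP accepts it.

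These points remove the claim of lost primary events and of bias. They leave the relabelling, the later event date, the tipping-point treatment, the unclear wording, and the two places with no stated imputation.

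**Conclusion.** Minor, but real. Condition 2 is written as an exclusive list, and nothing elsewhere classes the end-of-observation or withdrawal-from-follow-up visit as scheduled. In the primary analysis, on the plain reading, a sustained progression seen at withdrawal from FU1 still counts, but as an imputed event. It is dated at study withdrawal if treatment stopped for lack of efficacy; otherwise its status is varied in the tipping-point analysis. Events can actually be missed only under the literal reading of SAP 4.2.2, under the treatment-policy supplementary estimand if it does not inherit the imputation rules, or at end of observation without study withdrawal.

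The number affected cannot be derived from the documents. The 2 to 6 patients above rest on an assumed FU1 exit rate and on full attendance at exit visits, and should not be read as a count of lost events. A handful at most seems likely, with negligible effect on power.

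**What to change.** In SAP 4.2.1, reword condition 2 so that the confirmation visit must be a scheduled, treatment discontinuation, end-of-observation or withdrawal-from-follow-up visit. Make the same change to the confirmation sentences in SAP 4.2.2 and 4.4.4. Keep the other three conditions as they are. Add to SAP 4.2.2 that its imputation applies only to progression still unconfirmed after this rule. A progression observed for at least 84 days is then a confirmed event dated at onset, stays out of the tipping-point analysis, and counts under the treatment-policy supplementary estimand without needing an imputation rule.

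The cost is a few sentences before unblinding and one visit-type filter in the derivation program. The assessments are already in the schedule, so no new data are needed.

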Appendix 2: Schedule of Activities: Follow-Up 1 (and PDP OCR) (cont.)

	FU1 ^a						Delayed Dosing Visit ^b	Unsched. Visit ^c	Tx Discon. Visit ^d	EOO or WD from FU	
	Follow-up	PDP OCR									
Dose Visit	Visits every 12 wk (± 7 d)	1			N ^e						
Study week		1	2	3	n	n					
(Window in days)		0	2	12	n	n+ 12wk					
			±2	±7	±5	±7					
Concomitant medications ^r	x	x	x	x	x	x	x	x	x	x	
Adverse events ^s	x	x	x	x	x	x	x	x	x	x	
Mandatory MRI (every 48 weeks) ^t	(x)	(x)			(x)				x	x	
ADA sample (serum) ^u	x	x			x				x		
PK sample (serum) ^v	x	x	x	x	x				x		
Biomarker plasma and serum samples ^w		x	x	x	x					x	
RBR RNA and RBR plasma samples (optional) ^x		x	x	x	x					x	
Digital outcome assessments (Floodlight RPM) (optional) ^y	x	---	---	---	---	---	---	---	---	---	
Hepatitis B virus DNA ^z (if required)	x	x		x	x	x			x	x	

9-HPT = 9-Hole Peg Test; ADA = anti-drug antibody; Discon. = discontinuation; eCRF = electronic Case Report Form; EDSS = Expanded Disability Status Scale; EOO = end of observation; FU = follow up; HBcAb = hepatitis B core antibody; HBsAg = hepatitis B surface antigen; MFIS = Modified Fatigue Impact Scale; MRI = magnetic resonance imaging; MS = multiple sclerosis; MSIS-29 = Multiple Sclerosis Impact Scale-29; Neuro-QoL-UE = Quality of Life in Neurological Disorders-Upper Extremity Function; OLE = open-label extension; PDP OCR = post-double-progression ocrelizumab; PGIC-F = Patient Global Impression of Change for Fatigue; PGIC-UL = Patient Global Impression of Change for Upper Limb Function; PK = pharmacokinetic; PML = progressive multifocal leukoencephalopathy; PRO = patient-reported outcome; RBR = Research Biosample Repository; SDMT = Symbol Digit Modalities Test; Tx = treatment; Unschd. = unscheduled; WD = withdrawal; Wk = week; (x) = every 48 weeks.

Note: All assessments should be performed on the day of the scheduled visit, unless otherwise specified. On infusion days, all assessments should be performed prior to dosing, unless otherwise specified. For more information regarding eligibility for and duration of PDP OCR and FU1, see Sections 3.1.1.3 and 3.1.1.4, respectively. See Figure 2 for information regarding how a patient proceeds through the different study phases (including FU1 and PDP OCR).

Appendix 2: Schedule of Activities: Follow-Up 1 (and PDP OCR) (cont.)

- ^a The FU1 phase will run in parallel with the double-blind treatment phase until 144 weeks from randomization for each patient *or until the primary analysis*. Scheduled visits will be performed every 12 weeks and will include both efficacy and safety assessments. For patients receiving PDP OCR, patients must sign the optional PDP OCR informed consent form. Patients who experience a double-progression event during the double-blind treatment phase will be given the option to switch to PDP OCR after they have completed at least 120 weeks of double-blind treatment. PDP OCR treatment phase will continue until the end of the OLE phase. Assessments in FU1 and PDP OCR phases that only need to be performed annually are marked in brackets (x).
- ^b A delayed dosing visit will be performed and recorded in the Delayed Dosing Visit eCRF when dosing cannot be administered at the scheduled dosing visit. Other tests or assessments may be performed as appropriate.
- ^c Assessments at unscheduled (non-dosing) visits may be performed as clinically appropriate.
- ^d Patients who discontinue study drug prematurely from the PDP OCR treatment phase will return to the clinic for a treatment discontinuation visit.
- ^e The PDP OCR can be terminated at any time up to the date at which the last data point is collected for the primary analysis (see Section 3.1.1.3). The assessments required for N represent the typical schedule of assessments for the PDP OCR phase. If the study ends for any reason or the patient must be withdrawn from treatment, a treatment discontinuation visit should be performed.
- ^f Must be obtained and documented in written form before any study-specific screening procedure and initiation of study treatment and PDP OCR (if applicable).
- ^g Questionnaires will be self-administered prior to the administration of study treatment. The questionnaires should be completed before the patient receives any information on disease status, prior to the administration of non-PRO assessments, and in the following order each time, whenever possible: ABILHAND, Neuro-QoL-UE, PGIC-UL, MFIS, PGIC-F, MSIS-29, and EQ-5D-5L. During FU1 and PDP OCR they will be completed every 48 weeks, starting Week 0 of FU1. EQ-5D-5L will only be completed during PDP OCR.
- ^h Includes pulse rate, and systolic and diastolic blood pressure while the patient is in a seated position, and temperature. Temperature should be measured and recorded in patient's notes only. Blood pressure and pulse rate will be recorded on the appropriate eCRF. On ocrelizumab infusion visits, vital signs should be taken within 45 minutes prior to the methylprednisolone infusion. In addition, blood pressure and pulse rate should be obtained prior to start of infusion, every hour during the infusion, at the end of infusion and 1 hour after the end of the infusion. On non-infusion days, the vital signs may be taken at any time during the visit. Record abnormalities observed at baseline on the General Medical History and Baseline Conditions eCRF page. At subsequent visits, record new or worsened clinically significant abnormalities on the Adverse Event eCRF.
- ⁱ Perform a limited, symptom-directed examination at specified timepoints or as clinically indicated. Record new or worsened clinically significant abnormalities on the Adverse Event eCRF.

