3.1.1.4 Follow-Up 1 Phase

All patients who discontinue prematurely from the double-blind treatment phase will enter the FU1 phase, including patients who receive other DMTs for MS, commercial ocrelizumab, or no treatment. The FU1 phase will run in parallel with the double-blind treatment phase until 144 weeks from randomization for each patient *or until the primary analysis, whichever occurs earlier*. Scheduled visits will be performed every 12 weeks analogically to the initial (double-blind) schedule of activities and will include both efficacy and safety assessments (see [Appendix 2](#)). In the FU1 phase, patients will remain blinded to their original (randomized) treatment assignment. Patients who withdraw from treatment should be encouraged to remain in the study for the full duration of the FU1 phase. All patients who are ongoing in the FU1 phase at 144 weeks from randomization for each patient *or at the time of the primary analysis* will continue in the FU2 phase (see Section [3.1.1.6](#)).

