Appendix 1: Schedule of Activities: Double-Blind Treatment (cont.)

- ^d The assessments required for N represent the typical schedule of assessments for the double-blind treatment phase with Week 144 being the last visit. If the study ends for any reason or the patient must be withdrawn from treatment, a treatment discontinuation visit should be performed.
- ^e Must be obtained and documented in written form before any study-specific screening procedure and initiation of study treatment and PDP OCR (if applicable).
- ^f Questionnaires will be self-administered prior to the administration of study treatment. The questionnaires should be completed before the patient receives any information on disease status, prior to the administration of non-PRO assessments, and in the following order each time, whenever possible: ABILHAND, Neuro-QoL-UE, PGIC-UL, MFIS, PGIC-F, MSIS-29, and EQ-5D-5L. Questionnaires will be completed every 6 months during the double-blind treatment phase. EQ-5D-5L will not be completed at screening. PGIC-UL and PGIC-F will not be completed at screening and baseline.
- ^g Includes pulse rate, and systolic and diastolic blood pressure while the patient is in a seated position, and temperature. Temperature should be measured and recorded in patient's notes only. Blood pressure and pulse rate will be recorded on the appropriate eCRF. On ocrelizumab (or placebo) infusion visits, vital signs should be taken within 45 minutes prior to the methylprednisolone infusion. In addition, blood pressure and pulse rate should be obtained prior to start of infusion, every hour during the infusion, at the end of infusion and 1 hour after the end of the infusion. On non-infusion days, the vital signs may be taken at any time during the visit. Record abnormalities observed at baseline on the General Medical History and Baseline Conditions eCRF page. At subsequent visits, record new or worsened clinically significant abnormalities on the Adverse Event eCRF.

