4.4.1 Estimands for Continuous eCOA Endpoints

Estimand: The estimand is the mean difference in the endpoint between the experimental and control arms in patients with PPMS, including patients later in their disease course, and regardless of adherence to the randomized treatment or use of another MS DMT or commercial ocrelizumab.

Endpoints:

- Change from baseline to Week 120 in fatigue as measured by MFIS
- Change from baseline to Week 120 in a measure of manual ability for adults with upper limb impairments (ABILHAND)
- Change from baseline to Week 120 in the upper limb domain of a life quality measure for patients with neurological disorders (Neuro-QoL-UE)
- Change from baseline to Week 120 in the MSIS-29 physical domain score
- Change from baseline to Week 120 in the SDMT

Summary Measure and Primary Estimator: MMRM will be used to quantify mean difference in the endpoints between the experimental and control arms. The fixed effects in the model will include independent variables of randomized treatment, visit, baseline outcome, treatment-by-visit interaction, baseline outcome by visit interaction, along with the randomization stratification factors. An unstructured variance-covariance structure will be applied to model the within-subject errors across visits. The restricted maximum likelihood (REML) method will be used for estimation of variance components. In the case of non-convergence, compound symmetry will be used, together with a robust estimator of standard error (“sandwich” estimator).

The statistical significance of the estimated mean difference will be calculated by using the Wald test.

In order to estimate the estimand of interest, the following intercurrent event handling strategies will be applied:

Withdrawal from treatment and no initiation of another MS DMT or commercial ocrelizumab: All data available will be included in the analysis following the treatment-policy strategy.

Withdrawal from treatment and initiation of another MS DMT or commercial ocrelizumab: All data available will be included in the analysis following the treatment-policy strategy.

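### FU1 questionnaires are timed from the stopping date, so many patients who stop double-blind treatment before Week 120 have no scheduled Week 120 value for exploratory treatment-policy endpoints

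*Protocol*

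**What the plan says.** Protocol 3.1.1.4 sends every early stopper into FU1: "All patients who discontinue prematurely from the double-blind treatment phase will enter the FU1 phase". The phase has a fixed end for each patient: "The FU1 phase will run in parallel with the double-blind treatment phase until 144 weeks from randomization for each patient", or the primary analysis if that comes sooner. On visits it states: "Scheduled visits will be performed every 12 weeks analogically to the initial (double-blind) schedule of activities".

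The questionnaires follow a different clock. On double-blind treatment, Appendix 1 footnote f says "Questionnaires will be completed every 6 months during the double-blind treatment phase", and the table places them at the dosing visits (Weeks 24, 48, 72 and so on). In FU1, the Appendix 2 table marks ABILHAND, Neuro-QoL-UE, MFIS, MSIS-29, PGIC-F and PGIC-UL as 48-weekly, and footnote g fixes the starting point: "During FU1 and PDP OCR they will be completed every 48 weeks, starting Week 0 of FU1". The Appendix 2 column for end of observation or withdrawal from follow-up has no questionnaire entry. EDSS, 9-HPT and SDMT are marked at every 12-weekly FU1 visit.

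SAP 4.4.1 defines change from baseline to Week 120 in MFIS, ABILHAND, Neuro-QoL-UE, the MSIS-29 physical score and SDMT, irrespective of adherence or of other MS therapy. For both intercurrent events it says "All data available will be included in the analysis following the treatment-policy strategy". The estimator is an MMRM with visit as a factor and unstructured covariance. SAP 4.4.2 and 4.4.3 apply the same strategies to PGIC-UL, PGIC-F and the 7.5-point MSIS-29 worsening, tabulated by scheduled visit up to Week 120. The SAP gives no analysis visit window for these endpoints.

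**The concern.** A treatment-policy estimand at Week 120 needs outcomes at Week 120 from patients who have stopped treatment. The protocol keeps those patients in FU1 and sees them every 12 weeks, but it asks for the questionnaires on a cycle set by the date they stopped. Unless that date happens to lie 48 or 96 weeks before Week 120, no questionnaire is due at the estimand's time point. The patient attends and the instrument is simply not scheduled.

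At stake is how far the Week 120 results for fatigue, patient-reported hand function and MS impact can be read as treatment-policy effects.

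**Working it through.** The documents state no questionnaire-completeness figure, so there is nothing of the plan's own to reproduce.

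**Inputs.** Questionnaires every 48 weeks from FU1 Week 0 (Appendix 2, footnote g). FU1 visits every 12 weeks, ±7 days (Appendix 2). FU1 ends at Week 144 from randomization (Protocol 3.1.1.4). Target: Week 120 (SAP 4.4.1). Patients are assumed to remain in FU1 to Week 120.

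**Condition.** If FU1 Week 0 is at study week s, questionnaires fall at s + 48k for k = 0, 1, 2, …, up to Week 144. For s before Week 120, s + 48k = 120 has two solutions: k = 1 gives s = 72, and k = 2 gives s = 24.

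| FU1 entry week | Questionnaire weeks | Week 120? |
|---|---|---|
| 12 | 12, 60, 108 | no |
| 24 | 24, 72, 120 | yes |
| 36 | 36, 84, 132 | no |
| 48 | 48, 96, 144 | no |
| 60 | 60, 108 | no |
| 72 | 72, 120 | yes |
| 84 | 84, 132 | no |
| 96 | 96, 144 | no |
| 108 | 108 | no |

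For entry at Weeks 12, 36, 60, 84 or 108 (5 of 9), no FU1 questionnaire falls on the 24-weekly on-treatment calendar at all.

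**Share without a scheduled Week 120 value, stops before Week 120.** The distribution of stopping times is an assumption, so a range is shown.

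- Every stop at a dosing visit (24, 48, 72, 96): 2/4 = 50%.
- Equally weighted 12-week grid: 7/9 = 78%.
- Arbitrary dates, uniform over Weeks 0 to 120: 96% with a ±7-day window, 83% with ±28 days, 75% with ±42 days, 50% with ±84 days.

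**Weighting by time of stopping.** Suppose exponential discontinuation at annual rate d, with h = −ln(1 − d) and weight exp(−h·a/52) − exp(−h·s/52), where a is the grid point before s. The sample-size section's 10% annual dropout is borrowed for d. This is an assumption, because that figure is not stated to be a treatment-discontinuation rate.

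- 12-week grid, d = 10%: 19.65% of patients stop by Week 108 and 22.75% of them have a Week 120 questionnaire. Without one: 1000 × 0.1965 × (1 − 0.2275) ≈ 152 per 1000 randomized. For d = 5% to 20%: 78 to 284 per 1000.
- Dosing grid, d = 10%: 1000 × 0.1768 × (1 − 0.5122) ≈ 86 per 1000. For d = 5% to 20%: 45 to 160 per 1000.

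On the 12-week grid the share with a value stays at 22% to 23% across these rates, so the weighting barely moves it.

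**The case against.** **The share depends on when patients stop.** Infusions and re-treatment reviews are 24 weeks apart, so stops may cluster at dosing visits, where only half lack the value. Anyone stopping at or after Week 120 already has it. Counting those patients, 3/5 = 60% have the value on the dosing grid and 4/11 = 36% on the 12-week grid. This stands. A reader might infer that most discontinuers lack a Week 120 value; the documents do not support that without restriction, and on the dosing grid with late stoppers included it would be false. The SAP 4.1 rule placing discontinuation 24 weeks after the last dose does not settle the matter, because it is an analysis convention and not the FU1 entry date.

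**The model does not ignore these patients.** A reader might infer that the MMRM simply fills in Week 120 from patients still on treatment, so that the result is not a treatment-policy effect at all. That goes too far. The model conditions on each patient's own earlier scores, including those at the treatment discontinuation visit. It also uses off-treatment values that fall on modelled visits: Week 96 for entry at Week 48, Weeks 72 and 120 for entry at Week 24, and Week 120 for entry at Week 72. What remains is that Week 120 for the other stoppers is predicted under missing-at-random from relations estimated largely in patients still on treatment.

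**Section 3.1.1.4 says FU1 visits mirror the double-blind schedule.** That does not close the gap: the same sentence refers to Appendix 2, where the 48-week rule is explicit.

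**Conclusion.** The point holds for patients who stop double-blind treatment before Week 120. Between 50% (every stop at a dosing visit) and 78% (equally weighted 12-week grid) have no scheduled Week 120 questionnaire, and about 96% for arbitrary dates with a ±7-day window. The upper end depends on the unstated stopping-time distribution and on the absence of an analysis window. A window as wide as ±84 days would bring the arbitrary-date figure down to 50%.

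For these patients the treatment-policy label in SAP 4.4.1 is only partly backed by data and leans on missing-at-random. The PGIC and MSIS-29 worsening summaries in SAP 4.4.2 and 4.4.3 become observed-case.

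The consequence is limited. Every affected endpoint is exploratory and outside the hierarchical testing. A reader might take hand function to include the 9-HPT and so the primary endpoint; it does not, because EDSS and 9-HPT are assessed at every FU1 visit. SDMT shares the Week 120 estimand and is likewise unaffected. This is a worthwhile, low-cost improvement and not a threat to the trial's main conclusions.

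**What to change.** Amend Appendix 2 footnote g so that FU1 questionnaires follow weeks from randomization and explicitly include Week 120, completed at the FU1 visit nearest Week 120. Either Weeks 24, 72 and 120 or the 24-weekly double-blind calendar would do. Naming the week matters: a 48-week cycle counted from baseline gives Weeks 48, 96 and 144 and misses it. If FU1 visits run 12-weekly from an off-calendar start, the nearest visit can be up to 12/2 = 6 weeks away, so the SAP should also state an analysis window.

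**Cost.** No added visit. Keeping the questionnaire at FU1 entry and adding 24/72/120 means at most one more set per patient on the 12-week grid (entry at Week 60: 60, 72, 120 in place of 60, 108). The full 24-weekly calendar adds up to four (entry at Week 12: 12, 24, 48, 72, 96, 120, 144 in place of 12, 60, 108). It is also a protocol amendment, with the approvals described in Protocol 9.7.

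**Limit.** Values cannot be recovered for patients already past Week 120. For them, SAP 4.4.1 should state the missing-at-random assumption in place of an unqualified treatment-policy effect, and SAP 4.4.2 and 4.4.3 should label the summaries as observed-case.
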